## **16. Potential Benefits to Participants**

We do not know if all participants will receive personal benefits from taking part in this study. They may not benefit directly from joining the study. However, the potential benefits could include learning about mindfulness, reductions in stress, and improved emotional well-being. We also hope that the knowledge gained from this study may help others in the future.

## **17. Compensation to Participants**

If all study components are completed, participants will get \$100 worth in gift cards to compensate for their time and effort.

-After completion of the first study assessment, they will receive a \$25 gift card.

-After completion of the 4-week program and the second study assessment they will receive a \$50 gift card

-After completing the third and final study visit (1 month after completion of the program), they will receive a \$25 gift card.

If they do not finish the study, we will compensate them for the visits they have completed.

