#### **4. Study Endpoints**

##### **Primary endpoints:**

- Rates of recruitment and retention, adherence, and satisfaction. Adherence will be measured by the number of phone sessions attended and the frequency of self-reported completed home practice, both assessed at post-intervention assessments.
- Ratings of satisfaction, also assessed by survey in post-intervention assessments, will be measured with several questions, including one that reads “Overall, how satisfied were you with the stress reduction program”, “How satisfied are you NOW (after the stress reduction program) with your ability to manage the stress in your life?”, and “¿How much did the program helped you manage your stress?”
- We will also ask questions on satisfaction of the instructor and group setting: “Did you feel that the other participants cared about the group?”, “You felt that the instructor was very knowledgeable about the program”, “It was easy for you to communicate with the instructor”, and “Did you feel that the instructor cared about you?”

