provided and up to 10 reminders (via email, text or call) will be sent out to complete the assessment. The link to this last assessment will be sent out 1-month after completion of the intervention, but at least 3 weeks after the post-intervention assessment.

A weekly reminder will be sent out (the day prior to the session, via text and email) to remind participants to join the weekly Zoom call. Up to 10 reminders (on each occasion, via text, email or call) will be sent out to participants to complete the baseline, post-intervention, and 1mo post-intervention online questionnaire.

All gift cards will be electronic gift cards and the information will be sent out to participants via email or text.

Participants will be notified that all experiences shared during intervention sessions are considered confidential and should not be discussed outside of the group.

The following table shows the different measures being collected at the different time points (also see questionnaire/instruments provided for data collection at baseline, post-intervention, and 1mo post-intervention).

Timepoint	Baseline	Post intervention	1mo post intervention
Socio-demographics			
Age	X		
Gender	X		
Health insurance	X		
Education	X		
Income	X		
Municipality	X		
Food security	X		
SNAP	X		
Marital Status	X		
Perceived income	X		
Employment	X		
Mental health			
Depression (CESD-10)	X	X	X
PTSD (PCL-2)	X	X	X
Anxiety (GAD)	X	X	X
Perceived stress (PSS-4)	NA-included in screening	X	X
Resilience			
SP (Chen et al)	X	X	X
Mindfulness (FFMG-15)	X	X	X
Psychological flexibility (AAQ2)	X	X	X
Health behaviors			

PA (WHI)	X	X	
Perceived sleep qual	X	X	
Diet screener (Mattei et al)	X	X	
Emotional eating (TFEQ R18 V2)	X	X	X
Reward based eating (Reward based eating scale (RED))	X	X	X
Smoking	X	X	
e-cigarettes	X	X	
Clinical characteristics			
Self-reported diagnosis	X		
Medical care for mental health	X		
Medications for mental health	X		
Anthropometrics			
Self-reported blood pressure	X	X	X
Self-reported weight	X	X	X
Self-reported height	x	x	x
Self-reported pulse	x	x	x
Intervention			
Satisfaction		X	
Stress management		X	
Group and instructor environment		x	
Exercise that helped the most		X	X
Exercise most often practiced		X	X
# sessions attended		x	
Frequency of daily practice and duration		X	X
Overall feedback		X	

We have delineated a suicide prevention protocol as explained in section #19 of this document.

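### Section 17 leaves unclear whether a woman who stops sessions but answers the post-intervention survey is paid the $50, and that survey is the only source for satisfaction and sessions attended

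*Combined protocol and SAP*

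**What the plan says.** **Payment (Section 17).** There are three gift cards, $100 in total if everything is completed.

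- First card: "After completion of the first study assessment, they will receive a" $25 card.
- Second card: "After completion of the 4-week program and the second study assessment they will receive a" $50 card.
- Third card: "After completing the third and final study visit (1 month after completion of the program), they will receive a" $25 card.
- Closing line: "If they do not finish the study, we will compensate them for the visits they have completed".

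The section does not define program completion by a number of sessions, does not define a visit, and gives the second assessment no price of its own.

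**What the second assessment carries.** Section 4 makes satisfaction a primary endpoint: "Ratings of satisfaction, also assessed by survey in post-intervention assessments". On adherence it says: "Adherence will be measured by the number of phone sessions attended and the frequency of self-reported completed home practice, both assessed at post-intervention assessments". In the Section 6 schedule, satisfaction and the row for number of "sessions attended" are each marked at post-intervention only. The row "Frequency of daily practice and duration" is marked at post-intervention and again at 1 month.

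**Access and follow-up (Section 6).** The post-intervention questionnaire is opened after the last session, with up to 10 contact attempts or reminders. Nothing is said about women who stopped attending earlier.

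**The concern.** The other two cards reward giving data. The second, read literally, also rewards finishing the program. A woman who attends two sessions, stops, and then answers the post-intervention questionnaire has not met that condition as worded. The closing line suggests she is paid something but not how much. Staff could handle two such women differently, and neither woman could know in advance what she would receive.

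This matters because the primary objective is feasibility and acceptability. Women who stop are the ones most likely to show that the program was not feasible or acceptable. If they answer less often, satisfaction is estimated mainly from women who finished. Section 18 reports satisfaction and adherence for the total sample and plans an exploratory comparison of high and low adherers, which needs low adherers to respond. The mixed models in that section are for secondary outcomes. No handling of missing satisfaction data is described, and satisfaction has no second time point to draw on.

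**Working it through.** **1. The plan's own figure.** 25 + 50 + 25 = $100, which matches Section 17. The second card is 50/100 = 50% of the total and 50/(50 + 25) = 67% of what is still payable after baseline.

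**2. The payment rule for a woman who stops sessions and answers the second survey.**

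| Text in Section 17 | Result for her |
|---|---|
| $50 line, read literally | Condition not met, no $50 |
| $50 line, with completion read as a date (the four weeks are over) | $50 |
| Closing line on completed visits | Paid something, amount not stated |

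The section does not choose among these.

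**3. Which endpoint data depend on this survey.** From the Section 6 schedule: satisfaction, post-intervention only; number of sessions attended, post-intervention only; frequency and duration of home practice, post-intervention and 1 month. The dependence is therefore complete for satisfaction and for the attendance item, and partial for home practice. Section 4 names only post-intervention for both parts of adherence, so it differs from the schedule on home practice.

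**4. How large a response bias could be (illustration).** Only N = 30 comes from the documents. Assumed: 90% of women who finish answer; 90% of women who finish and 50% of women who stop are satisfied; they attend 4 and 1.5 sessions respectively.

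Formula: observed value = Σ(n × r × y) / Σ(n × r), summed over women who finish and women who stop, where n is the group size, r its response rate and y its mean.

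With 6 stopping and 24 finishing, true satisfaction = (24 × 0.9 + 6 × 0.5)/30 = 24.6/30 = 82.0%. True mean sessions = (24 × 4 + 6 × 1.5)/30 = 3.50. Women who finish return 24 × 0.9 = 21.6 surveys.

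| Response of women who stop | Surveys returned | Observed satisfaction | Overstatement | Observed mean sessions |
|---|---|---|---|---|
| 90% | 27.0 | (19.44 + 2.70)/27.0 = 82.0% | 0 points | 3.50 |
| 60% | 25.2 | (19.44 + 1.80)/25.2 = 84.3% | 2.3 points | 3.64 |
| 30% | 23.4 | (19.44 + 0.90)/23.4 = 86.9% | 4.9 points | 3.81 |
| 0% | 21.6 | 19.44/21.6 = 90.0% | 8.0 points | 4.00 |

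At 0% response, 3 women stopping gives 90.0 − 86.0 = 4 points, and 9 stopping gives 90.0 − 78.0 = 12 points. The sessions column assumes that attendance is taken from the survey alone.

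These figures show what differential non-response would do. They do not isolate the effect of the gift card.

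**The case against.** The best defence is that Section 17 is a general schedule with an exception. The three cards are listed under the case where all components are completed, and the closing line covers women who do not finish. The woman described above is such a case, so she would be paid, and only the amount is unstated. Completion may also mark a date, as it does in the timing of the third card. This stands in part: a reader might infer from the $50 line that women who stop forfeit the card, and the documents do not establish that. They do not rule it out either, because the closing line names no amount for the second assessment.

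Four other inferences are tempting and also go too far.

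- *That this is the only survey measuring adherence.* Home practice is asked again at 1 month. The statement holds only for satisfaction and number of sessions attended.
- *That women would over-report attendance to get the card.* Nothing says the card is released on self-reported attendance. Section 19 has the principal investigator present at all four sessions, so staff could know who attended, although no attendance log is stated.
- *That the rule depresses retention.* Retention is not defined, and no response data are given.
- *That the bias figures measure the effect of the card.* Women who stop may answer less often under any payment scheme, and up to 10 reminders partly offset non-response.

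The exposure of the secondary outcomes is also limited. Most of them are collected again at 1 month, with a card tied to that visit alone, and they are exploratory. Finally, paying for session time is a legitimate choice, since Section 17 says that payment is for time and effort. That does not require the survey payment to depend on it.

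**Conclusion.** The point holds as an ambiguity in the payment rule with a plausible route to bias in a primary endpoint. Section 17 does not say what a woman who stops sessions is paid for the second survey. On the literal reading of the $50 line she may lose the largest payment, for the only survey that records satisfaction and sessions attended.

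The direction is clear if women who stop are both less satisfied and less likely to answer: satisfaction is then overstated. The size is unknown. The 4 to 12 points at zero response, or 2.3 to 4.9 points at 60% to 30% response with 6 women stopping, rest wholly on assumed inputs. No share of them can be assigned to the card. A definite forfeit, inflated attendance reports and lowered retention are not shown by the documents. An amendment is still warranted, because it is cheap and removes both the ambiguity and one avoidable source of differential non-response.

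**What to change.** - In Section 17, replace the condition on the second card with, for example: *The $50 gift card is sent once the second assessment has been submitted, whatever number of sessions the participant attended.* This also removes the tension with the closing line.
- Make sure the consent form says the same. It was not among the material reviewed, so no mismatch is implied.
- In Section 6, state that women who stop sessions are still sent the post-intervention questionnaire and are told that they will be paid for it.
- A useful addition: name session records as the source for attendance, so that this part of adherence does not rest on survey response.

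**Cost.** A short amendment, plus at most $50 for each woman who stops and responds: 3 × 50 = $150 to 9 × 50 = $450 over the range used above, and less if the closing line was already meant to pay her. Attendance may be slightly lower once it is no longer tied to the card.

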## **18. Data Analysis, Management and Confidentiality**

Baseline descriptive statistics will include frequencies for categorical variables and means and standard deviations for continuous ones. Recruitment, adherence, retention, and satisfaction will be calculated for the total sample and will be explored by sociodemographic characteristics (i.e., age, income, employment, and education level). Changes in each secondary outcome will be evaluated using mixed

---

linear regression models controlling baseline covariates. We will conduct exploratory analyses among those with high levels of adherence (vs. low). STATA version 17 and SAS version 9.4 will be used.

Sample size considerations are driven by publications regarding pilot study planning. A minimum of 12 individuals per group is recommended for feasibility and precision around the estimates. Other MBCT pilot studies have included a similar sample size. This sample size suits the goals of this study to assess feasibility.

All study staff will be up to date with the Collaborative Institutional Training Initiative (CITI) Human Subjects trainings and will be trained for all protocols, including informed consent and data collection. The research team will maintain all responses and documents confidential. Individuals participating in the intervention will be informed that information disclosed within the intervention sessions is considered confidential and should not be repeated outside of the group. The data collected will only be used for research purposes. Only the research team will have access to the files. The electronic consent form and eligibility criteria will remain stored electronically. Identifiable information will not be shared to anyone and will be kept in a password-protected computer at Emory University and in the PI's OneDrive/SharePoint files.

## **19. Provisions to Monitor the Data to Ensure the Safety of Participants**

The screening and online survey will collect data on psychological distress, resilience, health behaviors, sociodemographic characteristics, and physical measurements (height, weight, waist circumference, and blood pressure), which will be entered real-time in REDCap (HIPPA compliant). The electronic consents and study files will be stored in the PI's (Emory University's) OneDrive and SharePoint platforms (HIPAA compliant). All data and project files will only be accessible by research study members. Access to any study documents are password protected and secure laptops.

Research staff will be trained on identification and report of adverse events. All participants receive an information sheet on mental health resources in Puerto Rico during their screening. The PI of the study will be present in all 4 weekly sessions to assess intervention fidelity. Any reports by participants of minor discomfort or any observations of a potential adverse event, whether directly related to the protocol or not, will be recorded and reported to the IRB in order to determine whether a formal report should be submitted. Serious adverse event will be reported immediately. Participants are those with elevated stress, however, they would be screened out (excluded) if they have major depression symptoms. Regardless, we have designed a suicide safety protocol:

If a participant reports suicidal ideation at any point during the study (e.g., intervention session or study visit), research staff will contact the participant and follow the following steps.

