#### **5. Study Intervention/Design**

This is a one-arm intervention study that will explore if a 4-week MBSR program is feasible and acceptable among young women in Puerto Rico with elevated stress. The intervention consists of 4 weekly virtual sessions and daily mindfulness exercises at home (between 5-16min of duration each, according to participant's availability). The participants will also complete three study assessments: baseline, post-intervention, and 1-month post-intervention. All study measures at all time points will be done online through questionnaires to be filled out by participants.

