Individuals will receive the 4-week tailored intervention in groups (3 waves of approximately 10 participants each; these may be stacked, overlapping, or following completion of each group, according to the instructor's availability). All weekly sessions will be delivered via Zoom. My team and I have the expertise and are equipped to recruit and implement the telephone-delivered program given our prior virtual studies in Puerto Rico and US Latinxs during the COVID-19 pandemic. Once in the intervention, participants will join one session weekly (on Zoom) and will receive access to online audio files, which are the daily practice exercises to be done at home.

Each session has a duration of 1hr (except the first session which is longer due to introductions and describing the program's logistics and expectations). The sessions follow a brief check-in, lecture on the week's topic, and guided practice. For the audio files, for each exercise, participants will have the opportunity to select a short version of the practice (5-8min) or a longer version (12-16min) according to their daily availability. The following table outlines the 4-week MBSR session topics and daily home-practice exercises.

Session	Topic	Home exercise
Week 1	Orientation; Introduction to stress and its consequences	Awareness of breathing
Week 2	Awareness of sensations	Body Scan
Week 3	Thoughts are not facts	Awareness of thoughts
Week 4	Recap; Mindful eating, mindful walking	Awareness of eating

After completion of the intervention, participants are encouraged to continue doing the mindful daily exercises at home by accessing the audio files. Following the last session, participants will be given access to the online questionnaire for the post-intervention measures, which will include the Contact information form. Research staff will have 10 attempts (via email, text or call) to contact participants and remind them to fill out the questionnaire.

1mo post-intervention, participants will be contacted to complete the third and final assessment, an online questionnaire, which will also include the Contact Information Form. The link to the survey will be

---

**Protocol Title:** Shift-and-persist and cardiometabolic markers among women in Puerto Rico: a pilot of a mindfulness-based trial

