## **15. Risk to Participants**

There may be side effects from the mindfulness program that are not known at this time. The most common risks and discomforts expected in this study are the time commitment for the weekly sessions and the completion of the study assessments. The mindfulness intervention that is being tested may not work for study participants and they may not perceive any benefits from the intervention. Researchers may ask questions about stress and stress management that may upset some participants. Interviewers are trained on cultural sensitivity and how to minimize any discomfort, including handling sensitive questions and emotional reactions. We will provide a toll-free phone number that individuals may call for any emotional or psychological advice or referrals at any time (from Línea PAS). Línea PAS is a 24hr 365days/year phone line responding to individuals with suicidal behavior and mental health disorders. It offers crisis counseling and emotional support, screening, psychiatric and psychological evaluation, and referrals (all free of charge). In addition, information on resources to coordinate mental health services will be provided to all prior to completing the screening questionnaire (see Mental Health Services document). Lastly, as with any study collecting identifiable information, there is a risk of loss of confidentiality but every effort will be made to keep all personal information confidential by use of id codes, password protected data files and analysis of de-identified data. Data on criminal or civil records, or any sensitive or personal information that may lead to such, will not be collected.

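### Adverse effects are captured only through participant reports and staff observation, and the schedule lists no question on unwanted effects, so harm is likely to be under-counted

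*Combined protocol and SAP*

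**What the plan says.** Section 15 (Risk to Participants) accepts that harm is possible: "There may be side effects from the mindfulness program that are not known at this time".

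Section 19 sets out how it would be found. "Research staff will be trained on identification and report of adverse events". The rule for what they log begins "Any reports by participants of minor discomfort or any observations of a potential adverse event, whether directly related to the protocol or not, will be". Whatever is logged goes to the IRB, and serious events are reported at once. No script, scheduled question or frequency is given. The investigator attends the sessions, but the stated purpose is fidelity: "The PI of the study will be present in all 4 weekly sessions to assess intervention fidelity".

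Section 5 says how data are collected: "All study measures at all time points will be done online through questionnaires to be filled out by participants". In the Section 6 schedule, the intervention block covers satisfaction, stress management, group and instructor environment, the most helpful and most practised exercises, sessions attended, practice frequency and duration, and overall feedback. Overall feedback is marked at post-intervention only.

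Exposure continues after the last session, when "participants are encouraged to continue doing the mindful daily exercises at home by accessing the audio files" (Section 6).

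**The concern.** The plan acknowledges side effects that are not yet known, but the text schedules no question that would find them. What gets recorded depends on a woman mentioning a problem or on staff noticing one. Both become less likely once the group sessions end, and for a woman who has stopped attending.

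Acceptability is part of the primary objective. If the pilot reports high satisfaction beside few or no adverse effects, a reader will take the second figure as evidence that the program is well tolerated. Under passive capture it would be weak evidence of that, and it would tell the designers of a larger trial little about what to expect.

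**Working it through.** The plan states no adverse-event rate, capture rate or safety threshold, so it has no figure to reproduce. The check is a reading of the text, followed by a calculation for scale.

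**Reading the text: is there a scheduled question on unwanted effects?**

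- Section 19: records reports and observations; no scheduled question.
- Section 6, sessions: "The sessions follow a brief check-in". Its content is not defined, and it ends with session 4.
- Section 6, schedule: no row for unwanted effects or for reason for stopping. At 1 month the intervention block still asks which exercise helped most, which was practised most and how often, but overall feedback is not repeated.
- Section 6, reminders: up to 10 contacts by email, text or call for each questionnaire. Their stated purpose is completion.
- Section 4: the satisfaction questions shown concern satisfaction, stress management, help, the group and the instructor. None shown asks about harm.
- Section 14: women may leave at any time, and staff may remove a participant for lack of commitment. Recording a woman's own reason for leaving is not mentioned.
- Sections 6 and 18: CESD-10, PCL-2 and the GAD scale are collected at all three assessments. They belong to the secondary outcomes, whose change is analysed with mixed models. This measures worsening distress but does not link it to a session or exercise, and a group mean can hide one woman who worsened.

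**Scale: what a zero count would mean**

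Input: n = 30 (Section 12). With no events in n women who were all asked and all answered, the exact one-sided 95% upper limit is 1 − 0.05^(1/n).

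- n = 30: 1 − 0.05^(1/30) = 9.5%.
- n = 24 (an assumed response, for illustration): 1 − 0.05^(1/24) = 11.7%. This describes women like the 24 who answered. The other 6 are unknown and could by themselves be 6/30 = 20% of the sample.

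Now suppose a share c of true events is recorded. A recorded rate of at most 9.5% corresponds to a true rate of at most 9.5%/c. If the true rate is 10%, the chance of recording nothing is (1 − 0.10c)^30. Both c and the 10% are assumptions.

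| Share captured, c | Upper limit on true rate if 0 of 30 recorded | Chance of recording none if true rate is 10% |
|---|---|---|
| 1 | 9.5% | 0.90^30 = 4.2% |
| 0.5 | 19.0% | 0.95^30 = 21.5% |
| 0.25 | 38.0% | 0.975^30 = 46.8% |

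The table shows how the meaning of a zero depends on c. It does not estimate c for this study.

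**The case against.** The strongest reply is that the schedule lists domains, not items, and refers to instruments that are not reproduced. Section 4 introduces its satisfaction questions as examples, so an adverse-effect item could exist in the actual questionnaire. That stands. A reader might infer that nobody is asked about harm, but the documents do not show this; they show only that no such row or procedure is described.

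Other channels also exist: the check-in, staff trained to recognise adverse events, reminder contacts that may be by call, a crisis line and resource sheet, and overall feedback. A reader might infer that a woman who stops attending passes out of view. The text does not say that she is dropped from the questionnaires or reminders, so that is too strong. What remains is that none of these channels is described as asking every woman the same question about unwanted effects.

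It can also be said that worsening distress is measured, and that harm causing dropout or dissatisfaction would lower the primary endpoints. Both are true and soften the point. Neither identifies the program as the cause, and low retention without reasons cannot separate upset from lack of time.

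A further tempting inference is that the distress scores will not be looked at for safety. The documents do not support that either: Section 19 names distress data, entered in real time, within the safety section. It does not say whether or how they are reviewed.

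**Conclusion.** The point holds as a design weakness that is cheap to correct. As written, the protocol captures adverse effects passively, and its schedule lists neither an unwanted-effect question nor a reason for stopping. Under-counting is likely, especially after session 4 and among women who stop attending, so a low count could not be read as absence of harm.

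The size cannot be given. The 9.5% limit for 0 of 30 applies only if all 30 women are asked and answer, and the figures for incomplete capture rest on assumed rates. A reader might infer that harm will certainly be missed, or missed by a known amount; the documents support neither. The conclusion assumes that the questionnaires follow the schedule. If they already contain such an item, what remains is to state it in the protocol and plan its reporting.

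**What to change.** Add to the post-intervention and 1-month questionnaires, sent to all enrolled women including those who stopped attending:

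1. a short closed item asking whether any session or home practice caused unwanted or upsetting effects, with severity and whether it led her to stop;
2. for women who missed sessions or stopped, the main reason.

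Beside the satisfaction results, report the number with any such effect among women who answered. Show the number who started and the number who did not answer separately, and do not count non-responders as unaffected: dividing by all who started would bring the under-count back among the women of most interest.

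The investigators should also state in Section 19 whether and how the distress data it names are reviewed for safety. This is a request for clarification; what any such review should consist of is for them to decide.

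The cost is a slightly longer survey at two time points, some non-specific complaints to sort through, and an IRB amendment.
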